## 2 STUDY OBJECTIVES AND ENDPOINTS

Objectives	Endpoints
Primary Objective: 

1. To assess the differences in endogenous glucose production in subjects with type 2 diabetes treated for 4 weeks either with ORMD-0801 or matching placebo following an intravenous infusion of [6,6-2H2]-glucose tracer using AUC(0-last).

	Primary Endpoint: 

1. Difference in endogenous glucose production between active and placebo as measured by the glucose with tracer attached using AUC(0-16) as the primary parameter.

Secondary Objectives: 

1. To compare the change from baseline in HbA1c levels measured at Week 4 in type 2 diabetic patients treated for 4 weeks with either ORMD-0801 or matching placebo.

2. To compare the change from baseline in plasma glucose levels measured at Week 4 in type 2 diabetic patients treated for 4 weeks with either ORMD-0801 or matching placebo.

3. To compare the change from baseline in ketone levels measured at Week 4 in type 2 diabetics treated for 4 weeks with either ORMD-0801 or matching placebo.

4. To compare the change from baseline in FFAs measured at Week 4 in type 2 diabetics treated for 4 weeks with either ORMD-0801 or matching placebo.

5. To compare the change from baseline in TC, LDLC, HDLC, and TG measured at Week 4 in type 2 diabetics treated for 4 weeks with either ORMD-0801 or matching placebo.

6. To assess the differences in endogenous glucose production in patients with type 2 diabetes treated for 4 weeks either with ORMD-0801 or matching placebo following an intravenous infusion of [6,6-2H2]-glucose tracer using other parameters including, but not limited to, Cmax, Tmax, Tlag and AUC over different time intervals.

7. To assess the safety of repeat administration of ORMD-0801 in patients with type 2 diabetes inadequately controlled on oral therapy.

	Secondary Endpoints: 

1. Mean changes in HbA1c from baseline to Day 29 of the treatment period.

2. Mean changes plasma glucose levels from baseline to Day 29 of the treatment period.

3. Mean changes in ketones from baseline to Day 29 of the treatment period.

4. Mean Changes in FFA from baseline to Day 29 of the treatment period.

5. Mean change in TC, LDLC, HDLC and TG from baseline to Day 29 of the treatment period.

6a. Difference in endogenous glucose production between active and placebo as measured by the glucose with tracer attached using other parameters including, but not limited to:

a. AUC(0-2), AUC(0-4), AUC(0-8), AUC(0-12),

b. AUC(2-16), AUC(4-16), AUC(8-16), AUC(12-16),

c. Cmax,

d. Tmax, and

e. Tlag.

6b. Difference in metabolites (β-hydroxybutyrate, acetoacetate, lactate, pyruvate, FFA, glycerol) and hormones (insulin, C-peptide, glucagon) between active and placebo using the same AUC intervals as endogenous glucose production.

7. Safety assessed by adverse event reporting including adverse events of special significance such as hypoglycemia.

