## 1 INTRODUCTION

Endogenous insulin – secreted by the  $\beta$ -cells of the endocrine pancreas – flows to the liver in the portal blood before reaching the systemic circulation through the hepatic veins. Following oral administration, the insulin in ORMD-0801 is absorbed through the gastrointestinal mucosa into the mesenteric veins (mostly, the superior mesenteric vein that drains blood from the jejunum and ileum) and reaches the liver *via* the portal vein, thereby mimicking the route of entry of endogenous insulin. The main action of insulin in the liver is to suppress glucose production; for this action, sensitivity is higher, and onset and offset time of this action are faster than for insulin stimulation of glucose uptake by peripheral tissues. First-pass extraction of insulin by the liver is 50-60%; recirculation raises this percentage to ~80%. As a consequence, portal plasma insulin concentrations normally are ~3-fold higher than peripheral insulin levels.

The hypothesis behind ORMD-0801 is that sufficient oral insulin survives gastrointestinal degradation to arrive at the liver where it inhibits glucose production and, through this effect, lowers fasting plasma glucose concentrations. As the majority of this exogenous insulin dose is degraded in the liver, the resulting systemic insulin levels may be only marginally increased, thereby avoiding the risk of hypoglycemia.

The use of glucose tracers is the standard non-invasive approach to measure endogenous glucose production (EGP). A tracer (in this protocol, [6,6-H2]-glucose, a stable isotope of glucose) infused intravenously at a constant rate will equilibrate with endogenous glucose across its distribution space within ~3 hours. From this time onward, the ratio of the tracer infusion rate to the plasma tracer/tracee ratio (as assayed by GCMS) measures EGP. As compared to placebo, oral insulin is expected to reduce EGP over the ensuing 13 hours of continued fasting. In patients with type 2 diabetes, EGP is known to be abnormally elevated and to contribute the hyperglycemia. Oral insulin is therefore addressing a key pathophysiological derangement of type 2 diabetes.

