**Table 1: Schedule of Events from Screening (Visit 0) to Discharge/End of Study (Visit 3, Day 29).**

	Screening	Treatment Period			Discharge / End of Study	Early Withdrawal
				TRACER Infusion		
Visit	0	1	2	3		
Week	-3 to -1	0	2		4	
Day	-21 to -7	0	14	28	29	
Informed Consent	X					
Inclusion/Exclusion	X	X				
Demographics (sex, age, race and ethnicity)	X					
Medical and Social History (including tobacco, alcohol, caffeine and drug use)	X					
Prior/Concomitant Medications	X	X	X	X	X	X
Physical Examination	X				X	X
12-lead ECG	X					
Height, Weight, BMI	X	X	X	X		X
Vital Signs	X	X	X	X	X	X
Chemistry, Hematology, Urinalysis	X				X 	X
Blood Collection for Plasma Glucose, Metabolites and Hormones	X			X	X	
Urine Drug Screen	X					
Serum Pregnancy Test	X					
Urine Pregnancy Test				X		
Breathalyzer	X	X	X	X	X	

	Screening	Treatment Period			Discharge / End of Study	Early Withdrawal
				TRACER Infusion		
Visit	0	1	2		3	
Week	-3 to -1	0	2		4	
Day	-21 to -7	0	14	28	29	
HbA1c	X	X	X	X	X	
Randomization		X				
Dispense study medication		X	X			
Collect study medication and review for compliance			X	X		
CRU Admission				X		
In-Clinic Dosing				X		
TRACER Infusion				X	X	
Blood Collection for Tracer Marked Glucose, Metabolites and Hormones				X	X	
Standard Meals				X	X	
CRU Discharge					X 	X
Adverse Events		X	X	X	X	X
End of Study					X	X

 Weight will be measured at each visit. Height will be measured and BMI will be calculated at Screening.

 Blood draw will be performed after the 16-hour infusion is complete.

 A blood plasma sample will be collected at Screening and during infusion for assessment of plasma glucose, metabolites and hormones according to [Table 2](#).

 Serum pregnancy test and urine pregnancy test will be performed for women of childbearing potential (WCBP) only.

 Subjects will be started on a 16-hour infusion of TRACER immediately following dosing. Refer to [Appendix A](#) (Guidelines for TRACER Infusion).

 Blood samples will be collected during the duration of infusion based on the blood draw schedule in [Table 2](#).

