## 6.2 Efficacy Assessments

### 6.2.1 16-Hour Tracer Infusion

A 16-hour tracer infusion will be performed after 28 days of treatment. The blood draw schedule during the tracer infusion is documented in [Table 2](#) in [Section 3.7](#) of the protocol. Based on the blood draws the values for the following lab tests will be obtained:

- Endogenous Glucose Production (glucose that is produced by the liver which has the tracer attached),
- Key metabolites ( $\beta$ -hydroxybutyrate, acetoacetate, lactate, pyruvate, FFA, glycerol), and
- Key hormones (insulin, C-peptide, glucagon).

For each of the lab tests, the following parameters will be derived (as appropriate):

- $AUC_{(0-16)}$ ,
- $AUC_{(0-2)}$ ,  $AUC_{(0-4)}$ ,  $AUC_{(0-8)}$ ,  $AUC_{(0-12)}$ ,
- $AUC_{(2-16)}$ ,  $AUC_{(4-16)}$ ,  $AUC_{(8-16)}$ ,  $AUC_{(12-16)}$ ,
- $C_{max}$  (endogenous glucose production only),
- $T_{max}$  (endogenous glucose production only), and
- $T_{lag}$  (endogenous glucose production only).

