### 8.3 Primary Efficacy Evaluation

The primary endpoint for this study is the difference in endogenous glucose production between active and placebo as measured by the glucose with tracer attached using  $AUC_{(0-16)}$ .

The primary endpoint will be analyzed using an Analysis of Variance model with treatment as the main effect.

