### 8.5.8 Handling of Missing, Unused, or Spurious Data

Descriptive statistics and listings will be provided for all data. No substitution of missing data will be used in any calculations. Data points that appear to be spurious will be investigated and will not be excluded from the listings. Influential cases will be handled in an appropriate statistical manner.

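### The primary AUC(0-16) starts about 3 hours before the tracer method, by the protocol's own account, measures EGP; AUC(3-16) is not listed

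*Combined protocol and SAP*

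**What the plan says.** - **Method (Section 1).** The constant-rate tracer "will equilibrate with endogenous glucose across its distribution space within ~3 hours. From this time onward, the ratio of the tracer infusion rate". The sentence goes on to divide this rate by the enrichment found in plasma and takes the result as EGP. Against placebo, "oral insulin is expected to reduce EGP over the ensuing 13 hours of continued fasting".
- **Start of infusion (Table 1, footnote 5).** "Subjects will be started on a 16-hour infusion of TRACER immediately following dosing". Appendix A gives a constant rate for 960 minutes and mentions no priming dose.
- **Primary endpoint (Synopsis, Sections 2 and 8.3).** "glucose with tracer attached using AUC (0-16) as the primary parameter", compared between arms by ANOVA with treatment as the only effect.
- **Primary objective (Synopsis, Section 2).** This names a different parameter: "glucose tracer using AUC(0-last)".
- **Analysed quantity.** Section 6.2.1 describes it as "Endogenous Glucose Production (glucose that is produced by the liver which has the tracer attached)", and Section 8.3 compares it "between active and placebo as measured by the glucose with tracer attached using" AUC(0-16). Neither refers to the ratio in Section 1.
- **Other windows.** Listed as secondary are 0-2, 0-4, 0-8, 0-12, 2-16, 4-16, 8-16 and 12-16. The lists in the Synopsis and Section 2 are open-ended; those in Sections 6.2.1 and 8.4.1 are not. AUC(3-16) is named nowhere.
- **Missing values (Section 8.5.8).** "No substitution of missing data will be used in any calculations".

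**The concern.** The primary parameter integrates over a period in which, on the protocol's own account, the measurement is not yet EGP. Time 0 is both the dose and the start of the infusion, so the first 3 hours contain tracer build-up.

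The direction of the error depends on a choice the plan leaves open:

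- **Rate over ratio (Section 1).** The ratio is zero before infusion, so EGP at time 0 cannot be computed and no substitution is allowed. At 45-150 minutes the ratio is still rising, so EGP is overstated.
- **Labelled-glucose concentration (the literal wording of Sections 2, 6.2.1 and 8.3).** The early hours are a rising curve from zero, which pulls the AUC down.

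The analyst would have to settle the quantity and the time-0 convention for the primary endpoint without guidance. Both arms share most of the artefact, so the expected harm is dilution of a true effect and some added noise. A false contrast would need plasma glucose to differ between arms at equal EGP.

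**Working it through.** **1. The protocol's own figure.** 16 h infusion - 3 h equilibration = 13 h, which reproduces Section 1. The measurable window is therefore hours 3 to 16.

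**2. What the listed windows cover.**

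| Window | Hours before 3 h | Share of window | Of the 13 h covered |
|---|---|---|---|
| 0-16 (primary) | 3 | 3/16 = 18.75% | 13/13 |
| 0-2 | 2 | 2/2 = 100% | 0/13 |
| 2-16 | 1 | 1/14 = 7.1% | 13/13 |
| 4-16 | 0 | 0% | 12/13 = 92.3% |
| 3-16 (not listed) | 0 | 0% | 13/13 |

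In Table 2, samples at 0, 45, 90, 120 and 150 min precede 3 h, which is 5 of 19. A 3-hour sample is drawn.

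**3. Size on the rate/ratio reading.** The documents do not say how complete equilibration is at 3 h. I assume one pool without a prime and a fraction p = 90, 95 or 99% equilibrated at 3 h, so k = -ln(1-p)/3 = 0.768, 0.999 or 1.535 per hour. Apparent EGP / true EGP = 1/(1 - exp(-kt)). At 45 min this is 2.28, 1.90 or 1.46; at 3 h it is 1.11, 1.05 or 1.01. At t = 0 it is undefined, so the AUC runs from 0.75 h, by trapezoid on the Table 2 times.

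| Quantity (p = 90 / 95 / 99%) | 0.75-16 h | 3-16 h |
|---|---|---|
| Overstatement of EGP | 7.65 / 4.65 / 1.89% | 1.12 / 0.43 / 0.06% |
| Apparent size of a true 10% reduction | 8.66 / 9.10 / 9.56% | 9.60 / 9.81 / 9.96% |
| False reduction, glucose 8 vs 9 mmol/L at equal EGP | 1.40 / 0.93 / 0.44% | 0.37 / 0.16 / 0.03% |

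Row 2 multiplies both EGP and k by 0.9, since turnover falls with EGP at a fixed pool. Row 3 multiplies k by 9/8, since the pool is smaller at the same EGP. For AUC(4-16) the overstatement is 0.54 / 0.17 / 0.01%. Between 0.75 and 3 h alone, the true 10% reduction shows as only 4.88 / 5.89 / 7.53%.

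**4. Size on the concentration reading.** The curve relative to plateau is 1 - exp(-kt). AUC(0-16) lies 8.36 / 6.53 / 4.49% below plateau, and AUC(3-16) 1.05 / 0.42 / 0.06% below. No between-arm consequence was computed for this reading.

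**5. Effect on the test (rate/ratio reading).** The protocol gives no variance or effect size (Section 8.2). The simulation used 4,000 runs, 20 per arm and a two-sample test, assuming a log-SD of EGP of 0.15 or 0.20, a log-SD of pool of 0.25 and 5% assay noise.

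- Rejection under the null: 0.049-0.053 over 0.75-16 h and 0.047-0.052 over 3-16 h.
- Power (%) for a 15% reduction, 0.75-16 h vs 3-16 h, at p = 90, 95 and 99%:
  - SD 0.15: 87.2 vs 90.1, 90.1 vs 91.7, 90.9 vs 90.9.
  - SD 0.20: 67.7 vs 69.5, 68.9 vs 69.9, 70.2 vs 70.2.

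The loss is 0 to 3 points; a repeat simulation gave about 0 to 4.

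**6. A harsher assumption.** Suppose hours 0-3 carry no treatment signal at all, and AUC(3-16) has an assumed standardized effect of 0.9 (power 0.81 with 20 per arm). Power on AUC(0-16) is then 0.65-0.79 if the hourly SD in hours 0-3 equals the later one (correlation 0.9 to 0), and 0.51-0.73 if it is twice as large. Under the step 3 model some signal remains in that period, so this case is pessimistic.

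**The case against.** The strongest reply is that this hardly touches the trial's question. The endpoint is a difference between randomised arms, the artefact is mostly common to both, the study is exploratory and its size was not based on power. The figures above bear this out: error rates hold and the power loss is small. That limits the severity. It does not supply a time-0 value or reconcile the primary window with Section 1.

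A second reply is that dose and infusion start together and Section 1 describes hepatic insulin action as fast, so leaving out the first 3 hours may discard real effect. In the same model, a 30% reduction confined to 0.5-4 h (an assumption) has a true 0-16 h size of 0.30 × 3.5/16 = 6.6%. The 0.75-16 h window shows 6.3-6.8%, and AUC(3-16) only 4.1-4.7%. That cost would be real, but Section 1 expects the effect in the 13 hours after equilibration.

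Third, AUC(4-16) is listed and slightly cleaner than AUC(3-16). That is true, and it makes a good sensitivity analysis. It is only a secondary parameter, however, and drops one of the 13 hours.

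Fourth, Section 8 defers details to a statistical analysis plan, and the early samples could support a non-steady-state calculation. No such calculation appears in the documents available. The rate/ratio figures above are for 0.75-16 h, of which 2.25/15.25 = 14.8% precedes 3 h, because AUC(0-16) has no computable starting value on that reading.

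**Conclusion.** The concern holds and should be fixed. The mismatch between Section 1 and the primary window is plain from the text, as is the lack of any rule for EGP before 3 hours. The consequence for the between-arm test is modest: a 10% reduction is diluted to 8.7-9.6%, type I error stays near 0.05, and about 0 to 4 power points are lost. These sizes rest on the one-pool model, 90-99% equilibration at 3 h, an effect constant over the whole infusion, and the assumed variances. The absolute EGP level is also misstated: 1.9-7.7% too high over 0.75-16 h on the rate/ratio reading, while on the concentration reading AUC(0-16) is 4.5-8.4% below plateau. I am confident about the contradiction and less certain about its exact size, which the documents cannot settle.

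**What to change.** In the Synopsis and Sections 2, 6.2.1 and 8.3:

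1. State that the analysed quantity is EGP, computed at each sample as tracer infusion rate divided by plasma tracer/tracee ratio.
2. Make AUC(3-16) the primary parameter, and replace AUC(0-last) in the primary objective with the same window.
3. Keep the listed AUC(4-16) as a sensitivity analysis, since the 3-hour figure is approximate.
4. Keep AUC(0-16) as supportive only, with a stated time-0 rule or a prespecified non-steady-state calculation for the first 3 hours.
5. Label EGP AUC(0-2), AUC(0-4), Cmax, Tmax and Tlag as descriptive.

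These are changes of wording, to be made before unblinding; no new sampling is needed. The price is that an effect in the first 3 hours after dosing no longer counts toward the primary result. The supportive analysis in item 4 would still show it.

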
### 3 INVESTIGATIONAL PLAN

#### 3.1 Overall Study Design and Plan

This study is designed to explore the efficacy of ORMD-0801 compared to placebo on endogenous glucose production in subjects with type 2 diabetes (T2DM). Subjects will undergo an initial Screening Visit (Visit 0) to establish their eligibility to participate in the study. At Visit 1 (2 weeks after the Screening Visit), qualifying subjects will be randomized to either ORMD-0801 (8 mg) or matching placebo, study medication will be dispensed and subjects will dose, twice a day, once in the morning prior to breakfast and once at night prior to bedtime. Doses will occur at 45 minutes ( $\pm$  15 minutes) before breakfast and no later than 10 AM each morning, and at 8 PM ( $\pm$  120 minutes) each night, and no sooner than 1 hour after dinner. Subjects will return to the clinic, 2 weeks later, for Visit 2. At this visit, subject compliance will be assessed, medication will be dispensed, a blood sample will be collected to measure HbA1c and subjects will be questioned for any adverse events. Subjects will be scheduled to return to the clinic in 2 weeks for morning admission (8 AM  $\pm$  120 minutes) to the PK unit (Visit 3). Subjects will be provided with standardized meals and the morning dose in-clinic. A light standardized dinner meal will be provided at 6 PM  $\pm$  30 minutes. At approximately 8 PM ( $\pm$  60 minutes, and no sooner than 1 hour after dinner), subjects will be dosed with their study medication and will be started on a 16-hour infusion of [6,6-H2]-glucose tracer. Blood samples will be collected to measure endogenous glucose (tracer attached), plasma glucose, metabolites and hormones for the duration of the infusion. Blood samples will be drawn at baseline (pre-infusion), 45, 90, 120 and 150 minutes, and 3, 4, 5, 6, 7, 8, 9, 10, 11, 12, 13, 14, 15 and 16 hours (see [Table 2](#) for blood draw schedule). Subjects will be required to remain fasting from the evening of Day 28 until the end of the infusion. Water intake will be unrestricted. On Day 29, blood sample will also be collected to measure HbA1c. Following completion of the infusion, the subjects will receive a standardized lunch and will be observed for an additional 6 hours. Prior to discharge, a physical examination will be performed, and blood/urine samples will be collected for safety chemistry, hematology and urinalysis, following which subjects will be discharged from the CRU and will exit the study.

#### 3.2 Screening/Visit 0 (Week -3 to -1, Day -21 to -7)

At the Screening Visit (Visit 0), potential subjects will be given a detailed oral presentation describing the nature, purpose, risks, and requirements of the study and will receive detailed written information. Subjects will be given ample time to consider participation and ask questions which will be adequately addressed by site personnel.

Once the subject is satisfied that he/she is willing to participate in the study, he/she will be asked to sign the study informed consent form (ICF) (refer to [Section 11.2.4](#) for further detail regarding the ICF). The investigational site personnel obtaining written consent from the subject will also sign the form to confirm consent has been obtained.

Once signed, the Investigator will retain the original ICF for the subject's study records and provide the subject with a signed copy. The investigator will verify that informed consent has been obtained from each subject prior to enrollment into the study and prior to the subject undergoing any study-related procedures.

Subjects will report to the clinic in morning following a 10-hour fast. Screening activities after obtaining informed consent will be conducted and consist of the following:

- Demographics (sex, age, race and ethnicity);
- Completion of medical and social history, including tobacco, alcohol, caffeine and drug use;
- Review of prior and current medications and supplements;
- Review of inclusion and exclusion criteria;
- Physical examination;
- 12-lead electrocardiogram (ECG);
- Measurement of height, weight and BMI;
- Measurement of vital signs (SBP/DBP and heart rate);
- Collection of fasted blood and urine samples for clinical safety labs:
  - Hematology, serum chemistry and urinalysis (see [Section 6.1.5.1](#) for list of tests);
  - HbA1c;
  - Urine drug screen;
  - Serum pregnancy test (women of childbearing potential/WCBP only);
- Breathalyzer;
- Blood plasma sample will be collected for the assessment of plasma glucose, metabolites and hormones listed in the footnote of [Table 2](#);
- Remind subjects to arrive fasting for Visit 1 in 2 weeks.

For subjects who meet eligibility criteria based on the Screening assessments, instruction will be provided on the following:

- the use of adequate contraceptive methods (see [Section 4.1](#)) for the duration of the study (Screening (Visit 0) through Visit 3);
- minimal use of concomitant medications during the study, if possible, and avoid prohibited medications as defined in [Section 5.6](#);
- maintenance of usual dietary habits and avoidance of drastic changes, such as a conversion to a vegetarian diet;
- restraint from excessive alcohol use or binge drinking during the study, and restraint from drinking alcohol from 72 hours prior to all study visits;
- restraint from excessive caffeine use (i.e., more than five cups of caffeinated beverages per day) during the study.

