Subject Selection Criteria	Inclusion criteria 

1. Male and female subjects aged, 18 - 70 years.

2. Established diagnosis of T2DM for at least 6 months prior to Screening, with HbA1c <math>\geq 7.5\%</math>. and <math>\leq 11\%</math>.

3. Stable dose of metformin (at least 1500 mg or maximal tolerated dose) for a period of at least 3 months prior to Screening.

4. Taking metformin only or metformin in addition to no more than two of the following: DPP-4, SGLT-2, or TZD.

5. Body mass index (BMI) of up to 35 kg/m^2 at Screening and stable weight, with no more than 5 kg gain or loss in the 3 months prior to Screening.

6. Renal function – eGFR <math>> 30</math> ml/min/1.73 m^2.

7. Females of childbearing potential must have a negative serum pregnancy test result at Screening.

- a. Females who are not of childbearing potential are defined as:
  - i. Postmenopausal (defined as at least 12 months with no menses in women  $\geq$  45 years of age);
  - ii. Has had a hysterectomy and/or bilateral oophorectomy, bilateral salpingectomy, or bilateral tubal ligation/occlusion at least 6 weeks prior to screening; OR
  - iii. Has a congenital or acquired condition that prevents childbearing.
- b. Females of childbearing potential agree to avoid becoming pregnant while receiving study treatment and for 14 days after the last dose of study treatment by complying with one of the following:
  - i. Practice abstinence† from heterosexual activity; OR
  - ii. Use (or have her partner use) acceptable contraception during heterosexual activity. Acceptable methods of contraception are‡:
    1. Single method (one of the following is acceptable):
      - a. Non-hormonal intrauterine device (IUD);
      - b. vasectomy of a female subject's male partner.
    2. Combination method (requires use of two of the following):
      - a. diaphragm with spermicide (cannot be used in conjunction with cervical cap/spermicide);
      - b. cervical cap with spermicide (nulliparous women only);
      - c. contraceptive sponge (nulliparous women only);
      - d. male condom or female condom (cannot be used together).

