#### **3.3.1 Visit 1 (Week 0, Day 0)**

Subjects will report to the clinic in morning following a 10-hour fast. At Visit 1, the following procedures will be performed:

- Review of inclusion and exclusion criteria;
- Review of prior and current medications and supplements;
- Measurement of vital signs (SBP/DBP and heart rate);
- Measurement of weight;
- Breathalyzer;
- Subjects will be randomized to either ORMD-0801 (8 mg) or placebo. Subjects will be instructed to dose twice a day. Doses will occur at 45 minutes ( $\pm$  15 minutes) before breakfast and no later than 10 AM each morning, and at bedtime (@ 8 PM  $\pm$  120 minutes) each night, and no sooner than 1 hour after dinner;
- Study medication will be dispensed;
- Blood sample will be collected to measure HbA1c;
- AEs/SAEs assessment;
- Remind subjects to arrive fasting for Visit 2 in 2 weeks.

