### 3.4 Tracer Infusion

#### 3.4.1 Visit 3 (Week 4, Day 28)

Subjects will report to the clinic in morning following a 10-hour fast. At Visit 3 (Day 28), the following procedures will be performed:

- Admission to the CRU (8 AM  $\pm$  120 minutes);
- Review of prior and current medications and supplements;
- Measurement of vital signs (SBP/DBP and heart rate);
- Measurement of weight;
- Breathalyzer;
- Urine pregnancy test (women of childbearing potential/WCBP only);
- Fasting blood sample will be collected to measure HbA1c;
- Study medication will be collected, and compliance will be reviewed;
- Subjects will be provided with a standard breakfast, lunch and dinner. The morning dose will be administered 45 minutes ( $\pm$  15 minutes) before breakfast and no later than 10 AM, in-clinic. A light standardized dinner meal will be provided at 6 PM  $\pm$  30 minutes.
- Subjects will be dosed in-clinic with either ORMD-0801 (8 mg) or placebo (@ 8 PM  $\pm$  60 minutes) and started on a 16-hour infusion of [6,6-H2]-glucose tracer immediately following dosing;
- Blood samples will be collected to measure endogenous glucose (tracer attached), plasma glucose, metabolites and hormones for the duration of the infusion. Blood samples will be drawn at baseline (pre-infusion), 45, 90, 120 and 150 minutes, and 3 and 4 hours (see blood draw schedule in [Table 2](#)). Subjects will be required to remain fasting from the evening of Day 28 (following dinner) until the end of the infusion;
- A backup blood sample will be collected at baseline (pre-infusion);
- AEs/SAEs assessment.

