 A standard breakfast, lunch, and dinner will be provided on Day 28. Subjects will fast following dinner on Day 28 until the completion of the 16-hour infusion on Day 29. After completion of the infusion, subjects will be provided with a standard lunch.

 Following the 6-hour observation and end of study procedures, subjects will be discharged from the CRU in the evening of Day 29.

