## 4 STUDY SUBJECT SELECTION

### 4.1 Inclusion Criteria

1. Male and female subjects aged, 18 - 70 years.
2. Established diagnosis of T2DM for at least 6 months prior to Screening, with HbA1c  $\geq 7.5\%$ . and  $\leq 11\%$ .
3. Stable dose of metformin (at least 1500 mg or maximal tolerated dose) for a period of at least 3 months prior to Screening.
4. Taking metformin only or metformin in addition to no more than two of the following: DPP-4, SGLT-2, or TZD.
5. Body mass index (BMI) of up to  $35 \text{ kg/m}^2$  at Screening and stable weight, with no more than 5 kg gain or loss in the 3 months prior to Screening.
6. Renal function – eGFR  $> 30 \text{ ml/min/1.73 m}^2$ .
7. Females of childbearing potential must have a negative serum pregnancy test result at Screening.
  - a. Females who are not of childbearing potential are defined as:
    - i. Postmenopausal (defined as at least 12 months with no menses in women  $\geq 45$  years of age);
    - ii. Has had a hysterectomy and/or bilateral oophorectomy, bilateral salpingectomy, or bilateral tubal ligation/occlusion at least 6 weeks prior to screening; OR
    - iii. Has a congenital or acquired condition that prevents childbearing.
  - b. Females of childbearing potential agree to avoid becoming pregnant while receiving study treatment and for 14 days after the last dose of study treatment by complying with one of the following:
    - i. Practice abstinence† from heterosexual activity; OR
    - ii. Use (or have her partner use) acceptable contraception during heterosexual activity. Acceptable methods of contraception are‡:
      1. Single method (one of the following is acceptable):
        - a. Non-hormonal intrauterine device (IUD);
        - b. vasectomy of a female subject's male partner.
      2. Combination method (requires use of two of the following):
        - a. diaphragm with spermicide (cannot be used in conjunction with cervical cap/spermicide);
        - b. cervical cap with spermicide (nulliparous women only);
        - c. contraceptive sponge (nulliparous women only);
        - d. male condom or female condom (cannot be used together).

†Abstinence (relative to heterosexual activity) can be used as the sole method of contraception if it is consistently employed as the subject's preferred and usual lifestyle and if considered acceptable

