## **5.3 Study Treatment Administration**

### **5.3.1.1 Double-Blind Treatment Administration**

All subjects will receive double-blind placebo or ORMD-0801 (8 mg insulin) twice a day, once in the morning and once in the evening, according to their randomization schedule from Visit 1 (Day 0) to Visit 3 (Day 28). Subjects will take one capsule (active or placebo), 45 minutes ( $\pm$  15 minutes) before breakfast and no later than 10 AM each morning, and one capsule at 8 PM ( $\pm$  120 minutes at Visits 1-2 and  $\pm$  60 minutes at Visit 3) each night, and no sooner than 1 hour after dinner.

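### The contraception instruction in Section 3.2 stops at Visit 3 and so omits about 13 of the 14 post-dose days that inclusion criterion 7b requires (minor internal inconsistency)

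*Combined protocol and SAP*

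**What the plan says.** Two places in the protocol state how long contraception should last.

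- **Section 3.2 (Screening/Visit 0).** Subjects who qualify on the Screening assessments are to be instructed on adequate contraception "for the duration of the study (Screening (Visit 0) through Visit 3"). The bullet refers to Section 4.1, but the reference follows the word for methods. The duration is then given separately, in the bullet's own terms.
- **Section 4.1, item 7b.** Women of childbearing potential must agree to avoid pregnancy while on study treatment and "for 14 days after the last dose of study treatment". The synopsis repeats the criterion: "for 14 days after the last dose of study treatment by complying with one of the following".

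The dates needed to compare them are also in the protocol.

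- Section 5.3.1.1 has subjects dosed "according to their randomization schedule from Visit 1 (Day 0) to Visit 3 (Day 28").
- Section 3.4.1 places the final dose in the clinic on Day 28: "Subjects will be dosed in-clinic with either ORMD-0801 (8 mg) or placebo (@ 8 PM", with a window of 60 minutes either side). Table 1 shows no in-clinic dosing on Day 29.
- Table 1, footnote 8, gives the end of Visit 3: "subjects will be discharged from the CRU in the evening of Day 29".

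Eligibility is reviewed at Screening and again at Visit 1, where Section 3.3.1 lists "Review of inclusion and exclusion criteria".

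**The concern.** The bullet and the criterion cover the same precaution but end on different dates, and the earlier date is the one sites are told to pass on. The omitted days are almost the whole of the post-dose period that the sponsor chose to require.

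That period has a purpose. Section 7.4.3 says that no animal reproductive studies have been done with ORMD-0801 and that its potential for fetal harm is unknown.

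No later procedure puts the instruction right. The lists for Visit 1, Visit 2, both days of Visit 3 and Early Withdrawal (Sections 3.3.1 to 3.6) contain no contraception line. The last scheduled pregnancy test is on Day 28 (Section 6.1.5.2), and no visit follows Day 29. A woman who relied on the bullet alone could believe that her obligation ended at discharge.

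**Working it through.** The plan gives no figure to reproduce. The check is calendar arithmetic for a subject who completes the study, with Visit 1 as Day 0.

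**Inputs**

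- Last dose: Day 28, about 20:00 (Section 3.4.1).
- Tracer infusion: starts immediately after that dose and lasts 16 hours (Section 3.4.1; Table 1, footnote 5). Appendix A gives the same timing, 20:00 to noon the next day.
- Observation after the infusion: 6 hours, then discharge (Section 3.5.1; Table 1, footnote 8).
- Required post-dose period: 14 days (Section 4.1, item 7b).

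**Steps**

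1. End required by 7b = last dose + 14 days = Day 28 20:00 + 14 d = Day 42 20:00.
2. End stated in Section 3.2 = end of Visit 3 = last dose + 16 h + 6 h = Day 28 20:00 + 22 h = Day 29 18:00.
3. Shortfall = 14 d − 22 h = 13 d 2 h, or in whole days 42 − 29 = 13.

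**Sensitivity to reading**

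- The 60-minute window around the evening dose does not alter the shortfall, because the infusion, the observation and the 14 days are all counted from the dose.
- If Visit 3 is read as Day 28 only, the shortfall is 42 − 28 = 14 days.
- No reading of Visit 3 reaches Day 42, because subjects leave the study at the Day 29 discharge (Section 3.1).
- No figure is given for early withdrawals. It would depend on the date of the last dose and on what an end at Visit 3 means for someone who never attends it.

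**The case against.** The strongest reply is that the bullet is an incomplete restatement of 7b and not a competing rule. It covers the study period and does not say that contraception may stop afterwards. A woman can satisfy both texts by continuing to 14 days after her last dose. The instruction also goes only to subjects found eligible, and a woman of childbearing potential is eligible only if she agrees to the 14 days. The bullet points to Section 4.1, where the 14-day rule stands in the same item as the methods. Section 3.2 also requires a detailed oral presentation and written information, and the consent form may give the right period. Finally, Section 7.4.2.1 requires pregnancies to be reported up to 30 days after study medication stops, which covers the whole 14-day period.

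Much of this stands, and it rules out two stronger readings that a reader might infer.

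- **That the protocol ends contraception at Visit 3, or has no effective post-dose rule.** The documents do not support this. Criterion 7b is unqualified, appears twice, and is reviewed twice before dosing.
- **That subjects were in fact told a period 13 days too short.** This cannot be shown. The other information given to subjects is not available here, so what they heard or read in total is unknown.

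The reply does not remove the inconsistency. The cross-reference is attached to methods, and the bullet then states its own duration with a defined end, so staff have no prompt to look for another. The eligibility reviews limit the consequence of the wording but do not make it correct. The reporting window detects pregnancies and does not prevent exposure.

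**Conclusion.** The point holds as an internal inconsistency of minor severity in a patient-safety instruction. For a completer last dosed on the evening of Day 28, the period stated in Section 3.2 ends on the evening of Day 29 and omits about 13 days of the 14 required after the last dose, which run to about Day 42.

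This rests on two assumptions: that the subject completes dosing on schedule, and that Visit 3 ends at the Day 29 discharge.

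The possible consequence is confined to women of childbearing potential, whose number among the approximately 40 subjects is not stated. They could be told an end date that is too early, although they must already have agreed to the correct one.

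A reader might take this as a criticism of the trial's design. It is not. The sponsor's choice is the 14-day rule, which is not in question, and the fault is that one bullet does not carry it through. No endpoint or analysis is affected, and nothing is concluded about the consent form.

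**What to change.** Extend the end of the Section 3.2 bullet so that the period reads: from Screening (Visit 0) through Visit 3 and, in women of childbearing potential, until 14 days have passed since the final dose (see Section 4.1, item 7b).

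This keeps the Screening start, which 7b does not state, and brings the end into line with 7b. Because the added period is counted from the last dose, it also serves women who withdraw early. A short reminder in Sections 3.5.1 and 3.6 would be useful but is optional.

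The cost is one phrase. Visits, procedures, endpoints and analysis are unchanged.
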